6.9.1. Rescue Medicine

There is no rescue therapy to reverse the AEs observed with isavuconazole, standard medical supportive care must be provided to manage the AEs.

7. DISCONTINUATION OF STUDY INTERVENTION AND PARTICIPANT DISCONTINUATION/WITHDRAWAL

7.1. Discontinuation of Study Intervention

It may be necessary for a participant to permanently discontinue study intervention. Reasons for permanent discontinuation of study intervention include the following.

- Premature withdraw from the study
- Has a successful overall outcome and has received a minimum of 7 days therapy after resolution of all clinical symptoms and physical findings of infection
- Has an unsuccessful overall outcome and requires alternative systemic antifungal therapy
- Completes 84 days of treatment (180 days for participants with IM, if applicable)
- Withdrawn from the study at investigator's or sponsor's discretion
- Intolerable AE
- Non-compliance
- Pregnancy

- Use of prohibited medication, including non-study systemic antifungal medication as described in [Section 6.9](#).
- Intercurrent illness requiring a change in participant management
- ALT or AST $\geq 10 \times \text{ULN}$

Note that discontinuation of study intervention does not represent withdrawal from the study. If study intervention is permanently discontinued, the participant should remain in the study to be evaluated for the following assessments. See the [SoA](#) for data to be collected at the time of discontinuation of study intervention and follow-up for any further evaluations that need to be completed.

The EOT assessments should be completed prior to premature withdrawal from study medication and, whenever possible, the Follow-up visit should be performed in all participants who received at least one dose of study medication. Survival status at Day 42, Day 84, EOT and Follow-up will also be collected.

In the event of discontinuation of study intervention, it must be documented on the appropriate CRF/in the medical records whether the participant is discontinuing further receipt of study intervention or also from study procedures, posttreatment study follow-up, and/or future collection of additional information.

7.1.1. Potential Cases of Acute Kidney Injury

Abnormal values in SCr concurrent with presence or absence of increase in BUN that meet the criteria below, in the absence of other causes of kidney injury, are considered potential cases of acute kidney injury and should be considered important medical events.

An increase of ≥ 0.3 mg/dL (or ≥ 26.5 $\mu\text{mol/L}$) in SCr level relative to the participant's own baseline measurement should trigger another assessment of SCr as soon as practically feasible, preferably within 48 hours from awareness.

If the second assessment (after the first observations of ≥ 0.3 mg/dL [or ≥ 26.5 $\mu\text{mol/L}$] in SCr relative to the participant's own baseline measurement) is ≥ 0.4 mg/dL (or ≥ 35.4 $\mu\text{mol/L}$), the participant should be discontinued from the study and adequate, immediate, supportive measures taken to correct apparent acute kidney injury.

Participants should return to the investigator site and be evaluated as soon as possible, preferably within 48 hours from awareness of the second assessment confirming abnormal SCr result. This evaluation should include laboratory tests, detailed history, and physical assessment. In addition to repeating SCr, laboratory tests should include serum urea, serum creatine kinase, and serum electrolytes (including at a minimum potassium, sodium, phosphate/phosphorus, and calcium), in addition to urinary dipstick, urine microscopic examination, and urinary indices. All cases confirmed on repeat testing as meeting the laboratory criteria for acute kidney injury, with no other cause(s) of laboratory abnormalities identified, should be considered potential cases of drug induced kidney injury irrespective of availability of all the results of the investigations performed to determine etiology of the

abnormal SCr. If ≥ 2 healthy participants are noted to have 2 consecutive SCr results of ≥ 0.3 mg/dL (or ≥ 26.5 μ mol/L), an assessment of whether the finding may be considered an adverse drug reaction should be undertaken.

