- k. EOT, Day 42, Day 84 and Follow-up assessments are required for all participants. Participants with a successful overall response are required to return for all these visits. Participants withdrawn from study intervention or with an unsuccessful overall response prior to Day 42 are required to return to conduct a clinic visit for the EOT visit but will not be asked to return for the Day 42 or Day 84 visits; however, the participant will be contacted by telephone to obtain survival status at these time points. For participants with IM, survival status on Day 126, Day 168 and Day 180 should be collected. A Follow-up visit will be performed 4 weeks (± 7d) after last dose of isavuconazole administration.
- l. If clinically indicated.
- m. If EOT occurs within 1 week of a scheduled visit, the visits and assessment can be combined; however, the schedule of assessments for EOT must be applied.
- n. 12-lead ECG is performed 15 minutes prior to the end of the first daily infusion or approximately 3 hours post oral dose during the treatment period.
- o. If the assessments are performed at screening, the additional assessments between Day 1 and Day 7 are not required.
- p. Applicable for participants continuing on study intervention.
- q. For participants with IA or other filamentous fungi infection other than IM, if study treatment needs to be extended to longer than 84 days, sponsor should be notified. For participants with IM, procedures on Day 84, Day 126 and Day 168 should follow requirements of Day 42, maximum of study treatment is 180 days or until EOT visit.
- r. GM antigen will be tested at screening. If clinically indicated, it can be tested during Day 1 to Day 7 for participants with IA only. Any 1 of the following: 1) A single serum or plasma value ≥ 1.0 ; 2) BAL fluid ≥ 1.0 ; 3) single serum or plasma: ≥ 0.7 and BAL fluid ≥ 0.8 ; 4) two consecutive values of either serum, plasma or BAL fluid between ≥ 0.5 to <1.0 (from two separate specimens of the same category) is considered a positive result. GM meeting the protocol defined requirements within 7 days prior to first dose of study drug are eligible for enrollment.
- s. Radiology imaging obtained within 1 week (if available) prior to screening could be used.
- t. Samples/assessments obtained within 72 hours prior to screening could be used.

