7.2. Participant Discontinuation/Withdrawal From the Study

A participant may withdraw from the study at any time at their own request. Reasons for discontinuation from the study include the following:

- Refused further follow-up;
- Lost to follow-up;
- Death;
- Study terminated by sponsor.

At the time of discontinuing from the study, if possible, an discontinuation visit should be conducted. See the [SoA](#) for assessments to be collected at the time of study discontinuation and follow-up and for any further evaluations that need to be completed.

The discontinuation visit applies only to participants who are enrolled/randomized and then are prematurely withdrawn from the study. Participants should be questioned regarding their reason for withdrawal.

If a participant withdraws from the study, they may request destruction of any remaining samples taken and not tested, and the investigator must document any such requests in the site study records and notify the sponsor accordingly.

If the participant withdraws from the study and also withdraws consent (see [Section 7.2.1](#)) for disclosure of future information, no further evaluations will be performed and no additional data will be collected. The sponsor may retain and continue to use any data collected before such withdrawal of consent.

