8.2.7. Survival Status

Survival status will be recorded until the Follow-up visit and be evaluated through EOT in all participants, irrespective of when treatment was discontinued. Detailed requirement should be performed as specified in [Section 1.3 SoA](#).

If the participant has died, the date and cause of death along with the reporting of SAE details will be recorded in the eCRF.

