8.4.1. Time Period and Frequency for Collecting AE and SAE Information

The time period for actively eliciting and collecting AEs and SAEs (“active collection period”) for each participant begins from the time the participant provides informed consent, which is obtained before undergoing any study-related procedure and/or receiving study intervention, through and including a minimum of 28 calendar days, except as indicated below, after the last administration of the study intervention.

Follow-up by the investigator continues throughout the active collection period and until the AE or SAE or its sequelae resolve or stabilize at a level acceptable to the investigator.

When a clinically important AE remains ongoing at the end of the active collection period, follow-up by the investigator continues until the AE or SAE or its sequelae resolve or stabilize at a level acceptable to the investigator and Pfizer concurs with that assessment.

For participants who are screen failures, the active collection period ends when screen failure status is determined.

If the participant withdraws from the study and also withdraws consent for the collection of future information, the active collection period ends when consent is withdrawn.

If a participant permanently discontinues or temporarily discontinues study intervention because of an AE or SAE, the AE or SAE must be recorded on the CRF and the SAE reported using the CT SAE Report Form.

Investigators are not obligated to actively seek information on AEs or SAEs after the participant has concluded study participation. However, if the investigator learns of any SAE, including a death, at any time after a participant has completed the study, and they consider

the event to be reasonably related to the study intervention, the investigator must promptly report the SAE to Pfizer using the CT SAE Report Form.

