8.4.3. Follow-Up of AEs and SAEs

After the initial AE or SAE report, the investigator is required to proactively follow each participant at subsequent visits/contacts. For each event, the investigator must pursue and obtain adequate information until resolution, stabilization, the event is otherwise explained, or the participant is lost to follow-up (as defined in [Section 7.3](#)).

In general, follow-up information will include a description of the event in sufficient detail to allow for a complete medical assessment of the case and independent determination of possible causality. Any information relevant to the event, such as concomitant medications and illnesses, must be provided. In the case of a participant death, a summary of available autopsy findings must be submitted as soon as possible to Pfizer Safety.

Further information on follow-up procedures is provided in [Appendix 3, Section 10.3](#).

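### Protocol 7.1.1 sends potential kidney-injury cases out of the study, although 7.1 keeps participants who stop drug under survival follow-up

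*Protocol*

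**What the plan says.** Protocol 7.1.1 (Potential Cases of Acute Kidney Injury) asks for a repeat creatinine after a rise of at least 0.3 mg/dL over the participant's own baseline. If the second assessment is at or above 0.4 mg/dL, "the participant should be discontinued from the study and adequate, immediate, supportive measures taken to correct apparent acute kidney injury".

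The parent section, 7.1, deals with stopping drug. It says "Note that discontinuation of study intervention does not represent withdrawal from the study", asks that such a participant stay in the study, and adds "Survival status at Day 42, Day 84, EOT and Follow-up will also be collected".

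Leaving the study is handled separately in 7.2, under the words "Reasons for discontinuation from the study include the following". The reasons given there are refusal of further follow-up, loss to follow-up, death, and termination by the sponsor. Kidney injury is named neither there nor in the 7.1 list of reasons to stop drug.

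Elsewhere the protocol favours continued follow-up:
- Schedule of Activities, footnote k: "EOT, Day 42, Day 84 and Follow-up assessments are required for all participants", with telephone contact for survival status in those withdrawn from drug before Day 42.
- Section 8.2.7: "Survival status will be recorded until the Follow-up visit and be evaluated through EOT in all participants, irrespective of when treatment was discontinued".
- Section 8.4.1 collects adverse events "through and including a minimum of 28 calendar days, except as indicated below, after the last administration of the study intervention".
- Section 8.4.3 says of reported adverse events that "the investigator must pursue and obtain adequate information until resolution, stabilization, the event is otherwise explained, or the participant is lost to follow-up".

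**The concern.** The protocol treats stopping drug and leaving the study as two different acts, and 7.1 requires the site to record which one applies. Section 7.1.1 uses the language of leaving the study inside the section on stopping drug, and no text reconciles the two.

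The distinction affects the analysis. SAP 2.2.2 defines the Day 42 and Day 84 mortality estimands with a treatment policy strategy, so survival status after stopping drug is needed. Protocol 9.3.1 and SAP 5.3 count a participant as a death in crude mortality when the last known survival status precedes the landmark day (or is missing) and the last assessment also falls before it (SAP 5.3: on or before). If a site took 7.1.1 at its word and made no further contact, a living participant would meet both conditions. The Day 42 rate is the key secondary endpoint.

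**Working it through.** **Text comparison.** Four features suggest that 7.1.1 was meant to stop drug only.
1. It sits under the heading on discontinuation of study intervention.
2. A comparable laboratory trigger, ALT or AST at or above 10×ULN, appears in 7.1 as a reason to stop drug.
3. Sections 4.1 and 7.2.1 also keep participants who stop drug in follow-up.
4. Section 7.1.1 still speaks of healthy participants, although the trial enrols patients with invasive fungal disease. The amendment history gives a template update as the reason for adding the section.

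**Size per case.** Inputs: 66 treated participants (protocol 9.5), and 19% Day 42 mortality on isavuconazole in SECURE (protocol 2.2.4), used for illustration only.
- One living participant counted as dead: 1/66 = 1.52 percentage points.
- Illustrative deaths: 0.19 × 66 = 12.5, taken as 13.
- Exact (Clopper-Pearson) 95% limits for x of n: the 0.025 quantile of Beta(x, n − x + 1) and the 0.975 quantile of Beta(x + 1, n − x).
- 13/66 = 19.7% (10.9 to 31.3).
- 14/66 = 21.2% (12.1 to 33.0).

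**Which stopping days are exposed.** Suppose the Follow-up visit is made and is the last contact. It falls 28 ± 7 days after the last dose, so between stop + 21 and stop + 35.
- The whole window precedes the landmark when stop + 35 < landmark.
- Status is secured when stop + 21 ≥ landmark.

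| Landmark | Whole window earlier | Timing decides | Status secured |
|---|---|---|---|
| Day 42 | stop by Day 6 (42 − 35 = 7) | Days 7 to 20 | from Day 21 (42 − 21) |
| Day 84 | stop by Day 48 (84 − 35 = 49) | Days 49 to 62 | from Day 63 (84 − 21) |

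**Scheduled chemistry visits after Day 1** (Schedule of Activities: Days 7, 14, 28 and 42). With the stop on the nominal visit day, Follow-up falls as follows:
- Day 7: Days 28 to 42
- Day 14: Days 35 to 49
- Day 28: Days 49 to 63
- Day 42: Days 63 to 77

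Only the Day 7 and Day 14 stops can put Follow-up before Day 42. All four put it before Day 84. Allowing 2 days for the repeat creatinine moves the windows to Days 30–44, 37–51, 51–65 and 65–79, and the same conclusions hold.

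**The case against.** The best reply is that this is loose wording with little practical reach.

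- Section 7.1 does not forbid withdrawing someone from the study. Its own list includes withdrawal at the investigator's or sponsor's discretion, and both lists are open-ended. This is true, but a discretionary exit does not reconcile a specific instruction to remove the participant with a rule that those who stop drug remain in the study.
- Several provisions protect follow-up. Section 7.1.1 itself brings the participant back for evaluation, 7.1 makes the site record the level of discontinuation, 7.2 ends data collection only when consent is also withdrawn, and footnote k covers all participants. This stands, and it is why the effect is zero when the planned contacts are made.
- The death rule has two conditions, and adverse event follow-up under 8.4.3 could produce an assessment after the landmark. This also stands. It narrows the exposure to sites that end contact, and no loss of adverse event follow-up is claimed here.
- The Kaplan-Meier analysis censors at the last known alive day (SAP 5.3), so a false death would not enter it. This helps with detection, but it is a sensitivity analysis. The crude rate is the main analysis.
- The section speaks of potential cases and apparent injury. The trigger is a second creatinine at the threshold, not a confirmed diagnosis.

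**Conclusion.** The instruction in 7.1.1 is wrong as written and conflicts with 7.1. Severity is minor.

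The size is 1.5 percentage points of crude mortality for each living participant whose contact ends before the landmark day. The documents give no rate of kidney injury and none is assumed, so the number of such cases is unknown. It is zero if sites make the contacts already planned. If Follow-up is the last contact, Day 42 mortality is exposed only for stops before Day 21. Day 84 mortality is exposed for stops by Day 48 and depends on visit timing for Days 49 to 62. The per-case figure rests on 66 treated participants, and the 19.7% to 21.2% example on a death rate near that of SECURE.

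**What to change.** Make three short edits, in a clarification letter or the next amendment:
1. In 7.1.1, say that the participant must be permanently discontinued from study intervention, in place of discontinuation from the study. The safety stop stays mandatory.
2. Add this creatinine criterion to the 7.1 list of reasons for stopping drug.
3. State in 7.1.1 that, unless consent is withdrawn, the following continue: the EOT and Follow-up visits, adverse event collection for at least 28 days after the last dose, and the survival contacts in footnote k (Day 42 and Day 84, plus Days 126, 168 and 180 for invasive mucormycosis).

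The cost is editorial. Every visit and contact named is already in 7.1, 8.4.1 or the Schedule of Activities, and no design figure changes.

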A 2-compartment population PK model was developed that included data from Phase 1 and Phase 3 studies. Chinese participants were found to have, on average, a 40% lower clearance compared with participants from Western countries. Monte Carlo simulations were then performed using mean population estimates. Based on the safety profile and PK/PD modeling and simulation for the antifungal activity of isavuconazole, the differences were not considered clinically significant. No dose adjustment is required for the Chinese population.

In the pivotal controlled study (SECURE Study, 9766-CL-0104), there were in total 26 Chinese participants who received at least 1 dose of study intervention, among them 10 participants were randomized to receive isavuconazole. Analysis of the efficacy in the China sub-group in SECURE Study showed the primary efficacy endpoints of all-cause mortality by Day 42 to be 10% (1/10) in the isavuconazole group and 25% (4/16) in the voriconazole group (difference of -15.0% with 95% CI [- 43.2%, 13.2%]). In general, efficacy of isavuconazole in Chinese participants was consistent with the findings in the overall population, indicating comparable mortality and overall response rates in the isavuconazole and voriconazole treatment groups. The safety profile was also comparable in Chinese participants to the overall population.

In summary, the clinical data of isavuconazole in Chinese population have been obtained from 46 Chinese participants including 36 healthy participants and 10 participants with IA. The overall PK, safety and efficacy of isavuconazole has been demonstrated in Chinese.

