5.1. Inclusion Criteria

Participants are eligible to be included in the study only if all of the following criteria apply:

Age and Sex:

1. Male and female Chinese participants aged ≥ 18 years at the timing of providing informed consent.

Disease Characteristics:

2. Participants must have proven, probable, or possible IFD caused by *Aspergillus* species, *Mucorales* species or other filamentous fungi, refer to the guidelines of EORTC/MSG (version 2019)³² or EORTC/MSG ICU (version 2021)³⁴ (see [Appendix 9, Section 10.9](#)).

Weight:

3. Participants with a body weight >40 kg at screening

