8.4.1.1. Reporting SAEs to Pfizer Safety

All SAEs occurring in a participant during the active collection period as described in [Section 8.4.1](#) are reported to Pfizer Safety on the CT SAE Report Form immediately upon awareness and under no circumstance should this exceed 24 hours, as indicated in [Appendix 3](#), [Section 10.3](#). The investigator will submit any updated SAE data to the sponsor within 24 hours of its being available.

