8.4.1.2. Recording Nonserious AEs and SAEs on the CRF

All nonserious AEs and SAEs occurring in a participant during the active collection period, which begins after obtaining informed consent as described in [Section 8.4.1](#), will be recorded on the AE section of the CRF.

The investigator is to record on the CRF all directly observed and all spontaneously reported AEs and SAEs reported by the participant.

As part of ongoing safety reviews conducted by the sponsor, any nonserious AE that is determined by the sponsor to be serious will be reported by the sponsor as an SAE. To assist in the determination of case seriousness, further information may be requested from the investigator to provide clarity and understanding of the event in the context of the clinical study.

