- The investigator will then record all relevant AE or SAE information in the CRF.
- It is not acceptable for the investigator to send photocopies of the participant's medical records to Pfizer Safety in lieu of completion of the CT SAE Report Form/AE or SAE CRF page.
- There may be instances when copies of medical records for certain cases are requested by Pfizer Safety. In this case, all participant identifiers, with the

exception of the participant number, will be redacted on the copies of the medical records before submission to Pfizer Safety.

- The investigator will attempt to establish a diagnosis of the event based on signs, symptoms, and/or other clinical information. Whenever possible, the diagnosis (not the individual signs/symptoms) will be documented as the AE or SAE.

Assessment of Intensity

The investigator will make an assessment of intensity for each AE and SAE reported during the study and assign it to 1 of the following categories:

- **Mild:** A type of AE that is usually transient and may require only minimal treatment or therapeutic intervention. The event does not generally interfere with usual ADL.
- **Moderate:** A type of AE that is usually alleviated with additional specific therapeutic intervention. The event interferes with usual ADL, causing discomfort, but poses no significant or permanent risk of harm to the research participant.
- **Severe:** A type of AE that interrupts usual ADL, or significantly affects clinical status, or may require intensive therapeutic intervention.

An event is defined as “serious” when it meets at least 1 of the predefined outcomes as described in the definition of an SAE, NOT when it is rated as severe.

Assessment of Causality

- The investigator is obligated to assess the relationship between study intervention and each occurrence of each AE or SAE. The investigator will use clinical judgment to determine the relationship.
- A “reasonable possibility” of a relationship conveys that there are facts, evidence, and/or arguments to suggest a causal relationship, rather than a relationship cannot be ruled out.
- Alternative causes, such as underlying disease(s), concomitant therapy, and other risk factors, as well as the temporal relationship of the event to study intervention administration, will be considered and investigated.
- The investigator will also consult the IB and/or product information, for marketed products, in their assessment.

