
Section # and Name	Description of Change	Brief Rationale	Substantial or Nonsubstantial
	withdrawal from study medication and, whenever possible, the Follow-up visit should be performed in all participants who received at least one dose of study medication. Survival status at Day 42, Day 84, EOT and Follow-up will also be collected.”	and the data collection for participants who have premature withdrawal.	
Section 7.1.1. Potential Cases of Acute Kidney Injury / Section 8.4.7. Disease Related Events and/or Disease Related Outcomes Not Qualifying as AEs or SAEs	Added mandatory language of Section 7.1.1. Potential Cases of Acute Kidney Injury and Section 8.4.7 Disease Related Events and/or Disease Related Outcomes Not Qualifying as AEs or SAEs	Protocol template update.	Nonsubstantial
Section 8.2.2. Radiological Assessment of Invasive Fungal Infection	Added “or MRI”.	Added to allow radiological assessment by MRI, especially for participants categorized as Non-LRTD.	Nonsubstantial
Section 8.2.5. Mycological Assessment of Invasive Fungal Infection/ Section 8.2.8. Investigator’s Assessment of Overall Response	Day 126 and Day 168 are added to the timepoints for Mycological assessments for IM participants	Keep consistency with SoA	Nonsubstantial
Section 8.2.3. Serum GM Antigen	Removed statement: “Outside of these time points, mycological assessments will be performed as clinically indicated and/or in line with standard clinical management. The results of all assessments performed during the study will be recorded on the eCRF .”	Removed redundant wording and keep consistency with SoA.	Nonsubstantial
Section 8.3.2 Vital Signs	Added “ear, or forehead”	Added to fit for the clinical practices at sites.	Nonsubstantial
Section 8.4. Adverse Events, Serious Adverse Events, and Other Safety Reporting/ Section 8.4.7.	Added text defining DRE and the conditions where Death will be reported as DRE instead of SAEs, which should be recorded and reported on corresponding CRF page.	Because IFD is serious/life-threatening, and death are defined as endpoints in this protocol. So it will not be captured as	Nonsubstantial

Section # and Name	Description of Change	Brief Rationale	Substantial or Nonsubstantial
Disease Related Events and/or Disease Related Outcomes Not Qualifying as AEs or SAEs		endpoints. But the cause of death should be reported as AE.	
Section 9.2 Analysis Sets	“GMe” is updated to “GM”	To correct a typo	Nonsubstantial

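### The kidney rule in Protocol 7.1.1 that counts across participants is limited to healthy participants, so it cannot apply in a trial that enrols only patients with IFD; the practical loss is small

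*Protocol*

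**What the plan says.** Protocol 7.1.1 has three steps for the individual participant:

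- A rise of at least 0.3 mg/dL over own baseline triggers a repeat test.
- If the second assessment is at least 0.4 mg/dL, the participant is discontinued.
- Cases confirmed on repeat testing, "with no other cause(s) of laboratory abnormalities identified, should be considered potential cases of drug induced kidney injury".

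Its opening sentence also classes qualifying cases without another cause as important medical events. One closing sentence counts across participants. It asks for an adverse-drug-reaction assessment when at least 2 "healthy participants are noted to have 2 consecutive SCr results of" at least 0.3 mg/dL (26.5 µmol/L).

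The population is defined in Protocol 5.1: "Participants must have proven, probable, or possible IFD caused by" *Aspergillus*, Mucorales or other filamentous fungi. There is no healthy cohort.

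SAP 6.6.2 (Assessment of Nephrotoxicity) counts participants with serum creatinine increases of at least 25%, 50% and 100% from baseline, over all post-baseline values and at EOT. It has no absolute-rise category.

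**The concern.** The primary objective is safety, and patients with renal impairment, including end-stage disease, are treated without dose adjustment (Protocol 4.3 and 6.6). The study is multi-center and has no external data monitoring committee (Protocol 10.1.5.1), so an instruction to look across participants has a purpose. The only numeric one in 7.1.1 is tied to people the trial does not enrol.

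The SAP table raises a separate, smaller matter. The protocol acts on absolute rises, while the table counts only relative ones. A participant whose rise reaches the size used for discontinuation could appear in none of the nephrotoxicity rows.

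**Working it through.** **1. Can the rule apply?** Protocol 2.1 describes the earlier Chinese data as coming from "46 Chinese participants including 36 healthy participants and 10 participants with IA". Healthy participants are thus the Phase 1 volunteers, set against patients. Nothing in the protocol supports a looser sense such as normal kidneys at baseline. Criterion 2 requires IFD, so the number of healthy participants is 0, and a count of at least 2 cannot be reached at any event rate.

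**2. Would deleting *healthy* repair it?** No. The earlier steps in 7.1.1 tie their thresholds to the participant's own baseline. The last sentence speaks only of SCr results of at least 0.3 mg/dL. Read literally, that is a creatinine level, and an ordinary one exceeds it: the eGFR equations in Protocol 10.6.2.1 use reference values of 0.7 mg/dL (women) and 0.9 mg/dL (men). The increase from baseline has to be written in.

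**3. Units.** With 88.4 µmol/L per mg/dL, 0.3 × 88.4 = 26.52 and 0.4 × 88.4 = 35.36. These match the protocol's 26.5 and 35.4 µmol/L.

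**4. When does an absolute rise miss the SAP's lowest row?** Relative rise = absolute rise / baseline. It is below 25% when baseline > rise / 0.25:

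- 0.3 / 0.25 = 1.2 mg/dL
- 0.4 / 0.25 = 1.6 mg/dL

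| Baseline SCr (mg/dL) | Rise of 0.3 | Rise of 0.4 |
|---|---|---|
| 1.0 | 30.0% | 40.0% |
| 1.2 | 25.0% | 33.3% |
| 1.6 | 18.8% | 25.0% |
| 2.0 | 15.0% | 20.0% |
| 3.0 | 10.0% | 13.3% |

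**5. Do other displays catch these rises?** In part. Actual values, change from baseline and flagged listings include them. The shift table may not: if baseline is already flagged high, a further rise is H to H and counts as no change. KDIGO grading (Protocol 10.6.3) catches some. As an illustration, assume age 60 and a rise from 1.7 to 2.1 mg/dL (0.4 / 1.7 = 23.5%, in no SAP row), with the creatinine-only equation:

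- Woman: 143 × (SCr/0.7)^-1.2 × 0.9938^60 goes from 34.0 to 26.3, G3 to G4.
- Man: 142 × (SCr/0.9)^-1.2 × 0.9938^60 goes from 45.6 to 35.4, staying in G3.

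The documents do not give the distribution of baseline creatinine, so the number of participants affected is unknown.

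**The case against.** The strongest reply is that the sentence is dormant and harmless. The amendment history records "Added mandatory language of Section 7.1.1. Potential Cases of Acute Kidney Injury" as a template update, so a clause about healthy participants may simply not concern a patient trial, and deleting it would be as sound as rewriting it. The sentence prompts an assessment and stops nothing. One confirmed, unexplained case already counts as potential drug induced kidney injury, so a rule that waits for two comes later. Important medical events would usually be handled as serious (Protocol 10.3.2), and "All SAEs occurring in a participant during the active collection period" go to the sponsor's safety group within 24 hours (8.4.1.1), which brings cases from all sites together.

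Other safeguards also remain:

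- "The investigator is obligated to assess the relationship between study intervention and each occurrence of each AE or SAE" (10.3.3).
- The sponsor conducts ongoing safety reviews (8.4.1.2).
- A confirmed creatinine rise leads to reflex cystatin C (10.6.1).
- An interim safety look is foreseen at about 28 participants (40% of 70); SAP 7.1 says it will be done, Protocol 9.4 that it may be.

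Most of this stands, and it is why the loss is small. It does not make the sentence work. Deletion would be consistent, but it would leave 7.1.1 without a group prompt, and rewording costs no more. The rewording adds that prompt. It also covers rises confirmed at 0.3 but below 0.4 mg/dL, if confirmation is read as reaching 0.4 on repeat. A rewrite that names nobody would help little, because no single investigator sees all sites. The fix therefore assigns the task.

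On the SAP, the percentage categories are legitimate and should stay. A count of rises confirmed on repeat is not proposed, because it would need a rule for which test is the repeat and within what interval.

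**Conclusion.** The point holds as a wording error in one operative safety sentence. As written the rule cannot fire, and this follows from the text without any assumed rate. The consequence is minor: one explicit prompt to look across participants is inactive, while handling of individual cases is intact. The SAP gap is certain as arithmetic (above 1.2 and 1.6 mg/dL) but of unknown frequency.

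A reader might infer more, and the documents do not support it:

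- *Kidney injury would go undetected.* It would not: the individual steps, causality assessment and expedited reporting all apply to patients with IFD.
- *The rises outside the percentage rows go unreported.* They do not: they reach listings and change-from-baseline summaries, and those recorded as AEs reach the TEAE tables.
- *The primary endpoint or sample size is affected.* Neither uses this rule.
- *The sentence was certainly left in by mistake.* The template origin fits that explanation but does not prove it.

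This is worth correcting, but it does not call for an amendment of its own.

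**What to change.** **Protocol 7.1.1.** Replace the last sentence with:

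> If ≥ 2 participants each have 2 consecutive SCr increases of ≥ 0.3 mg/dL (≥ 26.5 µmol/L) from their own baseline with no other cause identified, the sponsor's safety review will assess whether the finding may be an adverse drug reaction.

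The responsible party already exists: Protocol 8.4.1.2 refers to work done "As part of ongoing safety reviews conducted by the sponsor". The cost is one sentence. Protocol 10.1.1 requires IRB/EC approval of amendments, so bundle it with the next one.

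**SAP 6.6.2.** Keep the three percentage rows and add two counts: participants with any post-baseline SCr rise of ≥ 0.3 mg/dL, and with any rise of ≥ 0.4 mg/dL. Label them as laboratory criteria regardless of cause. They use creatinine data already collected and the all-post-baseline approach already in that section. The 0.4 row will not equal the number discontinued, because the protocol's step requires a second assessment.

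The downside is that the new rows will include small relative changes where baseline creatinine is high (0.3 / 5.0 = 6%). They should be read beside the percentage rows and the TEAE tables.
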